## **HYPOTHESES AND SPECIFIC AIMS**

**HYPOTHESIS:** The pro-inflammatory state of BPD subjects can delay, diminish or even thwart antidepressant monotherapy. Combination therapy of escitalopram + celecoxib will result in improved treatment outcomes (faster action, augmented response, and/or higher remission rates) for treatment-resistant BPD subjects. Response to antidepressant treatment in BPD subjects will be proportional to the change in pro-inflammatory status before and after treatment.

**SPECIFIC AIM #1:** Determine if combined pharmacotherapy of escitalopram + celecoxib will result in improved affective responses compared to escitalopram + placebo. Scores from the Short-Form McGill Pain Inventory will be used to control for variation in depression that could be attributed to the relief of physical pain resulting from administration of celecoxib.

**SPECIFIC AIM #2:** Determine whether combined pharmacotherapy of escitalopram + celecoxib causes any pharmacokinetic drug-drug interaction or poses safety/tolerability issues in terms of gastrointestinal bleeding or cardiovascular health. Clinical and laboratory assessments will be made throughout treatment and an adverse events inventory will be completed at each visit.

**SPECIFIC AIM #3:** Determine the blood concentration of pro-inflammatory biomarkers of all subjects before and after treatment. Determine whether there is a correlation between blood concentration of pro-inflammatory biomarkers and the psychiatric effectiveness of the combined treatment.

**SPECIFIC AIM #4:** Quantify the specific anti-inflammatory action of celecoxib by assaying for inhibition of PGE2. PGE2 concentrations will be measured from the blood of all subjects before and after treatment.

**HYPOTHESIS:** A chronic pro-inflammatory state leads to endothelial dysfunction, arterial stiffness, and dis-regulation of the autonomic nervous system with sustained sympathetic activation and diminished vagal tone.

**SPECIFIC AIM #5:** Determine whether endothelial dysfunction is present in BPD subjects and if this dysfunction will respond favorably to the combined treatment of escitalopram + celecoxib. The detection will be accomplished by means of arterial pulse wave analysis, velocity and heart rate velocity.

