## III. Second Tier Exploratory Endpoints

Our “second tier endpoints” are exploratory in nature. Our study is not powered for them since existing data in the literature is insufficient to calculate an accurate sample size for these endpoints.

1. We will seek to establish whether a specific psychiatric symptom profile may be associated with the anticipated differential mood improvement in response to escitalopram + celecoxib or escitalopram + PBO. To that end, additional rating instruments have been included (over and above the HAM scales) and detailed assessments will be made of symptom profiles obtained from the rating instruments.
2. We will assess the safety and tolerability of the combination treatment by means of an adverse events symptom checklist and by relevant laboratory measures (e.g., CBC, PT, PTT).
3. Assessment of the efficacy of celecoxib by measuring PGE2 response to assess the extent of COX-2 inhibition.
4. An assessment of blood levels of escitalopram and celecoxib will tell us if these two agents interfere or promote each other's uptake and/or clearance.

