At the Baseline visit, subjects will be reassessed for depression and associated symptoms. If subjects continue to score 18 or higher on the 17-item HAM-D scale, they will be randomized to receive escitalopram + celecoxib, or escitalopram + placebo in an assignment ratio 1:1. Subjects will then go on to complete assessments at Week 1, Week 2, Week 4 and Week 8. If the subject scores below 18 on the 17-item HAM-D scale at Baseline, he or she will be terminated from the study and classified as a placebo responder. At each of these visits, subjects will arrive 30 minutes before their scheduled appointment time, rest for 20 minutes in the exam room, and provide a saliva sample prior to undergoing any assessments. Terminated subjects will be offered conventional care at the same institution.

It is our desire to observe the diurnal nature of cortisol levels in saliva by measuring the patient's salivary cortisol levels at a time point prior to treatment and post treatment. At each of these two time points, we would collect saliva from the patient at five times during the day: upon awakening, approximately 30 minutes past awakening, before lunch, at approximately 3pm, and before bedtime. The patient would be required to do this at home and would then store the samples in their refrigerator until their next visit. Subjects will be provided with a log to record the exact time of saliva collection. We will be using salivettes purchased from Sarstedt Inc., and our Salivary Assay kits will be purchased from Salimetrics, LLC.

The overall study is powered for 90 subjects. We aim to randomize 70 subjects at LUMC. Approximately 30 subjects will be randomized by investigators at our sister site in Munich, Germany. At LUMC, 35 subjects will be randomized to each arm of the study. Subjects must complete 8 weeks of active medication to be considered study completers. We plan to enroll approximately 80 patients in anticipation of a 10% drop-out rate. The drop-out rate is based on our experience with our patient population over the past 5 years. If a subject drops out or is terminated after Week 6, their last observation will be carried forward in the analysis (LOCF). There are no healthy controls in this study because we already possess normative, untreated data for comparison.

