## ASSESSMENTS

### I. Psychometric Data Collection Instruments

Mini International Neuropsychiatric Interview (MINI)

Hamilton Rating Scales for Depression (HAM-D) and Anxiety (HAM-A)

Beck Depression Inventory (BDI); Beck Anxiety Inventory (BAI)

MADRS-Montgomery Asberg Depression Rating Scale (MADRS)

Columbia Suicide Severity Rating Scale (C-SSRS)

State/Trait Anxiety Inventory (STAI)

Spielberger Anger Expression Inventory (STAXI)

Inventory of Clinically Significant Upper and Lower GI events (CSULGIE)

Short-Form McGill Pain Inventory (MPI)

Perceived Stress Scale (PSS-14)

Quality of Life and Enjoyment Questionnaire (QLES-Q)

International Physical Activity Questionnaire (IPAQ)

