## DATA ANALYSIS AND STATISTICAL METHODS

### I. Statistical Analysis

Specific Aim 1 is to determine if combined pharmacotherapy of escitalopram + celecoxib will result in earlier and/or improved affective responses compared to escitalopram + PBO. Additionally, Specific Aim 1 seeks to control for pain perception in this analysis. For this aim, the patients in the two treatment arms will be compared on HAM-D, HAM-A, MADRS, BDI, and BAI scores. This will be accomplished with an analysis of covariance conducted at weeks 1, 2, 4 and 8. Baseline mood scores and McGill Pain Inventory scores will be used as covariates. In addition, the number of patients who are and are not classified as remitters at week 8 (those having a HAM-D score of 7 or less) will be tallied and cross-referenced with treatment group (escitalopram + celecoxib or escitalopram + PBO). The frequencies in the resulting 2-by-2 contingency table will be analyzed with the Pearson Chi-Square Test for Association.

For Specific Aim 2, dealing with treatment safety and tolerability, the numbers of patients who do and do not experience adverse events at weeks 1, 2, 4, and 8 will be tallied and cross-referenced with treatment group. The frequencies in the resulting 2-by-2 contingency table will be analyzed with the Pearson Chi-Square Test for Association. Additionally, to understand whether any pharmacodynamic interaction exists between escitalopram and celecoxib, blood levels of escitalopram and celecoxib drawn at weeks 4 and 8 will be compared for patients in the two treatment groups with an analysis of covariance using baseline levels as a covariate. If there is no pharmacokinetic interaction then we expect that there will be no statistically significant results for these analyses.

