All statistical analyses will be conducted using the latest version of SPSS software for Windows. If a subject drops out after completing 6 weeks on active medication (after randomization), we will use the last observation carried forward (LOCF method) to analyze the data. If a subject has completed at least one week on active medication after randomization, but drops out of the study at any time between week-1 and week-8, s/he will be included in the intent-to-treat analysis. Since this project seeks to provide proof-of-concept in bipolar depression, and is therefore exploratory in nature, we propose the tests of significance use a 0.05 alpha level. However, if this proposal develops further we may adjust our desired level of statistical significance to be in line with the number of tests so that the family wise Type I error rate could be held at 5%. This issue will be considered in the future.

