## II. Determination of Sample Size

Although a number of tests of statistical significance are planned for the proposed study, our required sample size is being based upon the primary outcome of treatment effect (Specific Aims 1). In looking at differences in mean HAM-D scores from the studies by Akhondzadeh et al. 5 and Mueller et al. 6 we found that the effect sizes of an antidepressant + anti-inflammatory agent over an antidepressant + placebo at week 3 of treatment were 0.53 and 0.52, respectively. In the proposed research we anticipate that the effect size will be slightly higher due to the fact that variation in depression scores attributable to baseline levels and pain perception will be eliminated in an analysis of covariance. Hence, we anticipate that the effect size will be about 0.60 for escitalopram + celecoxib over escitalopram + PBO. As noted earlier, we anticipate that the drug combination will lead to a therapeutic response that is earlier than what is normally seen at week-3 of treatment. We thus expect to see a treatment effect at week-2 of therapy, and expect that the magnitude of the effect will increase over the course of the study. The increasing separation between the different treatment groups is similar to what was found in the studies mentioned above which observed rising treatment effects during the course of therapy. From this, our computations indicate that a sample size of 45 patients per group will provide 80% power for an analysis of covariance to detect an effect size of 0.60 at week-2 of therapy using a 0.05 level of significance. Thus, a total of 90 patients completing treatment will be acquired for the proposed work. 30 of the total patients will be enrolled and randomized at our sister site in Munich, Germany. Given that the therapeutic effect size is expected to increase over time, the proposed sample size will be adequate throughout the course of the study. Subjects lost to attrition will be replaced.

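### Aim 2 asks about GI bleeding and cardiovascular safety, but the plan compares the arms only on patients with any adverse event

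*Combined protocol and SAP*

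**What the plan says.** All references are to the combined protocol and SAP.

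- **The question.** Under Hypotheses and Specific Aims, Aim 2 asks whether the combination causes a pharmacokinetic interaction or "poses safety/tolerability issues in terms of gastrointestinal bleeding or cardiovascular health".
- **The analysis.** The Aim 2 paragraph of "I. Statistical Analysis" gives one safety analysis: "the numbers of patients who do and do not experience adverse events at weeks 1, 2, 4, and 8 will be tallied" and set against treatment group. "The frequencies in the resulting 2-by-2 contingency table will be analyzed with the Pearson Chi-Square Test for Association". The paragraph's other analysis, an analysis of covariance on drug blood levels, serves the pharmacokinetic half of the aim.
- **What is collected.** The Schedule of Events has CSULGIE, the inventory of upper and lower GI events, at Screen 1, Baseline and every treatment visit. It has CBC/PT/PTT at Screen 1 and Weeks 2, 4 and 8. Brachial pressure is recorded at the SphygmoCor sessions (Baseline, Week 4 and Week 8).
- **What is promised.** Second Tier Exploratory Endpoints says that safety will be assessed by an adverse event checklist and "by relevant laboratory measures (e.g., CBC, PT, PTT"). It adds that the study is not powered for these endpoints.

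No section states a between-arm comparison of CSULGIE, CBC/PT/PTT, bleeding, blood pressure or cardiovascular events. The arterial measures belong to Aim 5, whose analysis is described as still being developed.

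**The concern.** The analysis does not address the outcomes that the aim names. In the any-event table, a patient with mild dry mouth and a patient with a GI bleed are the same "yes". Both arms receive open-label escitalopram, whose listed side effects already put patients in that category, so a GI excess on celecoxib partly falls on patients who are counted anyway. Under Safety Assessments and Adverse Events Monitoring, clinically significant worsening from the entry examination is recorded as an adverse event. That sends laboratory findings into the same pool and leaves smaller shifts in hematocrit, platelets or clotting times uncompared.

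At stake is whether the trial can report anything specific on the two risks it singles out. The plan itself says that an SSRI with a COX-2 inhibitor may induce a bleeding diathesis, and it notes the boxed cardiovascular warning on celecoxib.

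**Working it through.** **Inputs from the documents.** "a sample size of 45 patients per group will provide 80% power for an analysis of covariance to detect an effect size of 0.60" (Aim 1, Determination of Sample Size). Allocation is 1:1. On significance, "we propose the tests of significance use a 0.05 alpha level"; sidedness is not stated. GI bleeding odds ratios are 2.36 for an SSRI alone and 6.33 for an SSRI with an NSAID. The plan's own estimate of bleeding diathesis on the combination is at most 1 in 350.

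**Reproducing the plan's figure.** Two-sided, n per arm = 2(1.960 + 0.842)²/0.60² = 43.6, so 44. Power at 45 per arm is 80.4% by the noncentral t. The stated 45 is reproduced, and alpha is taken as two-sided. No sample size or event rate is given for the safety comparison.

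**Assumptions, not in the documents.** A proportion b of each arm has some non-GI event. A proportion g has a GI event, independently of the others. Both refer to whatever period the table covers; the text mentions one table for four visits, so per-visit or cumulative counting is unclear. Either way all event types are pooled.

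**Formulas.** Any-event rate = 1 − (1 − b)(1 − g). The shift between arms is therefore (1 − b)(g₁ − g₀). Rejection rates come from exact enumeration of the uncorrected Pearson chi-square at 45 per arm.

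**GI 5% to 15%:**

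| Other events, b | Any-event rate | Shift (points) | Any-event test significant |
|---|---|---|---|
| 20% | 24.0% to 32.0% | 8 | 14% |
| 30% | 33.5% to 40.5% | 7 | 11% |
| 50% | 52.5% to 57.5% | 5 | 7% |
| 70% | 71.5% to 74.5% | 3 | 7% |
| 80% | 81.0% to 83.0% | 2 | 6% |

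The same test on GI events alone is significant in 39% of trials (31% at 35 per arm, 39% at 50 per arm).

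**Using the documents' ratio.** Both arms take an SSRI, so the between-arm analogue is 6.33/2.36 = 2.68. Applied as an odds ratio to 5%: odds 0.05/0.95 × 2.68 = 0.141, which is 12.4%. The any-event test is then significant in 6% to 10% of trials for b from 70% to 20%, against 26% for GI events alone.

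**Other GI rates.**
- 2% to 6%: any-event 5% to 7%, GI alone 14%.
- 10% to 30%: any-event 36% at b = 20%, falling to 11% at b = 70%; GI alone 69%.

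**Overt bleeding.** At 1/350, the expected number in 45 celecoxib patients is 45/350 = 0.13. The chance of seeing even one is 1 − (349/350)^45 = 12%. With none seen, the one-sided 95% upper limit is 1 − 0.05^(1/45) = 6.4%.

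**The case against.** The strongest reply is that safety is openly exploratory and unpowered, so low power is no defect. That stands, and the point does not ask for power. At the plan's own bleeding rate no test would help. But exploratory status does not explain why the named outcomes have no by-arm summary at all.

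Second, serious GI events would not go unseen. "Adverse Events Reporting" records description, intensity, causality and seriousness, with summaries to the IRB and the Data Safety Monitoring Board. GI bleeding is a termination criterion, and raised blood pressure or decreased hematocrit is a suspension criterion. This is fair: "count the same" is true only inside the any-event table. These are monitoring provisions, however, and not comparisons between arms.

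Third, the dilution rests on assumed rates. This also stands. With few other events and common GI events the any-event test does respond: at b = 20% and GI 10% to 30% the shift is 16 points. Under independence, the share of extra GI events falling on patients already counted is b, which is half at 50% and only a fifth at 20%.

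A reader might also infer two stronger claims. One is that a non-significant table will be reported as proof of safety. The documents do not say so; the only null result that the Aim 2 paragraph interprets concerns drug levels. The other is that the odds ratio of 6.33 is the excess at issue between the arms. It is not: the control arm also takes an SSRI, the figure covers all NSAIDs, and the plan expects a much lower risk here.

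**Conclusion.** The mismatch is in the text and needs no assumption. Aim 2 names GI bleeding and cardiovascular health, the stated safety analysis pools all adverse events, and the specific data collected have no stated by-arm analysis.

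How much is lost depends on rates that the documents do not give. Assuming independence and 45 per arm, the any-event test is less sensitive than a GI-specific one in every setting above. The gap is largest in relative terms when other events are frequent. Even the GI-specific test stays below 80% power in all of them, so the gain is a direct estimate with its uncertainty and not a decisive test. For an exploratory endpoint this is a worthwhile correction and does not threaten the trial's primary question.

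**What to change.** In the Aim 2 analysis, add summaries by arm over the 8 weeks, each patient counted once:

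1. any CSULGIE event, and any bleeding event;
2. change from Screen 1 in hematocrit, platelet count, PT and PTT;
3. cardiovascular adverse events, and change from Baseline in brachial pressure.

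Give each as a risk difference or mean difference with a 95% confidence interval, exact for events. Keep the any-event table as a general description of tolerability. State that a non-significant result is not evidence of safety.

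This needs no change of analysis population, visits or treatment, because the measurements are already scheduled. The cost is analysis wording, a few more tables, and intervals that will be wide for rare events.

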## STUDY PROCEDURES

### Schedule of Events

Procedure	Screen 1	Screen 2	Baseline	Week 1	Week 2	Week 4	Week 8
Consent	X						
Assign Subject ID	X						
MINI	X						
HAM-D/HAM-A/MADRS	X*	X*	X	X	X	X	X
CGI/CSSRS/AdverseEvents/CSULGIE	X		X	X	X	X	X
Self-Assessment Packet			X	X	X	X	X
Dispense Study Medication		PBO	X	X	X	X	X
Physical Exam	X						X
Drug Screen and Pregnancy Test	X						X
Routine Clinical Labs	X						X
Research Blood Draw			X			X	X
CBC/PT/PTT Monitoring	X				X	X	X
Pulse Wave Analysis			X			X	X

Heart Rate Variability			X			X
Albuterol Challenge			X			X
Pulse Wave Velocity			X			X
Saliva Sampling		X	X	X	X	X

\*HAM-D only.

Routine Clinical Labs include complete blood count, complete metabolic panel, lipid profile and thyroid function.

The following assessments are included in the self-assessment packet:

- Beck Depression Inventory (BDI)
- Beck Anxiety Inventory (BAI)
- State/Trait Anxiety Inventory (STAI)
- Spielberger Anger Expression Inventory (STAXI)
- International Physical Activity Questionnaire (I-PAQ)
- Quality of Life and Enjoyment Questionnaire (QLES-Q)
- The Short-Form McGill Pain Inventory (MPI)
- Perceived Stress Scale (PSS-14)

Subjects will be treated as outpatients for a total of ten weeks. Subjects must complete at least six weeks to be regarded as completers. If a subject chooses to withdraw from the study on or after six weeks of treatment, he or she will be asked to complete end-of-study assessments at that time. Those results will be carried forward for the purpose of data analysis.

Subjects will not receive any other type of therapeutic intervention (e.g., psychotherapy) during participation in the study. Such options may be offered to them at the conclusion of the study, if appropriate.

Subjects who complete the study and respond favorably will remain under the care of the LUMC physician, if they wish.

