## **ADVERSE EVENTS REPORTING**

All AEs will be reported, regardless of whether the event seems related to the study drugs escitalopram and/or celecoxib. Study staff will also report AEs spontaneously reported by the patient and/or observed by the staff. Information that will be collected includes:

- A description of the event
- Start and stop date
- Action taken with regards to investigational product
- Outcome
- If the AE causes the patient to discontinue the study
- A statement reporting if the AE meets criteria for a Serious Adverse Event or not (see below)
- The investigator's assessment of the causal relationship between the event and the study drug
- Intensity of the AE
  - mild (awareness of sign or symptom, but easily tolerated)
  - moderate (discomfort sufficient to cause interference with normal activities)
  - severe (incapacitating, with inability to perform normal activities)

All serious adverse events (SAE) will be documented and reported to appropriate regulatory bodies. All adverse events will be summarized in a report at intervals requested by the IRB and the Data Safety Monitoring Board.

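### Aim 2's adverse-event tally has no stated safety population, denominator or cumulative rule, so some readings of it can understate a tolerability difference between the arms

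*Combined protocol and SAP*

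**What the plan says.** All references are to the combined protocol and SAP.

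- **I. Statistical Analysis, Specific Aim 2.** The safety comparison is specified as follows: "the numbers of patients who do and do not experience adverse events at weeks 1, 2, 4, and 8 will be tallied". These counts are split by arm, and the test is then named: "The frequencies in the resulting 2-by-2 contingency table will be analyzed with the Pearson Chi-Square Test for Association". The only other Aim 2 analysis concerns drug levels. The section does not say who is in the denominator, whether the count is per visit or cumulative, or how a patient already off study is treated.
- **I. Statistical Analysis, closing paragraph.** A patient with at least one week on active medication who leaves between Week 1 and Week 8 stays in the intent-to-treat analysis. The text neither names Aim 2 nor restricts this rule to efficacy.
- **II. Determination of Sample Size.** The target is stated as "a total of 90 patients completing treatment will be acquired for the proposed work", and "Subjects lost to attrition will be replaced". No exception is made for patients who stop because of an adverse event.
- **Adverse Events Reporting.** The items recorded for each event include "If the AE causes the patient to discontinue the study". No analysis uses this item.
- **Study Procedures, Schedule of Events.** End-of-study assessments are tied to one condition: "If a subject chooses to withdraw from the study on or after six weeks of treatment".
- **IV. Safety Assessments and Adverse Events Monitoring.** Formal monitoring is after weeks 1, 2, 4 and 8 and asks about the time since the previous visit. A physical examination and clinical laboratory tests are also done at termination.

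**The concern.** Aim 2 asks whether the combination causes tolerability problems. A count restricted to people still attending at a given visit, or to completers, is conditioned on having tolerated treatment so far. If one arm loses more patients to adverse events, the most affected patients leave its later counts, and replacements who supply a full set of visits enter. The remaining groups can then look alike when the randomised groups did not. Such a result could be reported as evidence of good tolerability.

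Two gaps do not depend on how the tally is read. Stopping because of an adverse event is a direct measure of tolerability and is already collected, but it is not compared by arm. And if the one-week minimum in the intent-to-treat rule governs Aim 2, patients who stop in the first week are left out under either a per-visit or a cumulative count.

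**Working it through.** **1. The plan's own figure.** There is none for the Aim 2 safety test. The sample size rests on efficacy: "a sample size of 45 patients per group will provide 80% power for an analysis of covariance". The target of that calculation is given as "to detect an effect size of 0.60 at week-2 of therapy using a 0.05 level of significance". Two-sided, n = 2(1.960 + 0.842)²/0.60² = 43.6, so 44 per group by the normal formula. The t-based calculation gives 44.6, rounded up to 45, with 80.4% power. The 45 reproduces. Randomising 90/(1 − 0.10) = 100 allows for the 10% drop-out given under Study Design.

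**2. Who is counted under each reading.**

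| Reading | Patient who stops for an adverse event |
|---|---|
| Per visit, attendees only | Absent from every later visit; the event itself may also be missed |
| Per visit, event counted at the visit where it arose | Counted once, absent afterwards |
| Completers only | Not counted |
| Cumulative, one-week minimum applied | Counted, unless stopping was in week 1 |
| Cumulative, everyone dosed | Counted |

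**3. Completers only against all randomised.** Inputs: 100 randomised and 90 completing, 45 per arm. Assumptions: replacement restores 45 completers in each arm, all ten leavers had an event, and 9/45 completers per arm (20%) had one. With d leavers in an arm, the proportion over all randomised patients is (9 + d)/(45 + d). The completers-only table is 20% v 20% throughout.

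| Leavers, by arm | All randomised | Difference (points) |
|---|---|---|
| 5 : 5 | 14/50 v 14/50 (28.0% v 28.0%) | 0 |
| 7 : 3 | 16/52 v 12/48 (30.8% v 25.0%) | 5.8 |
| 8 : 2 | 17/53 v 11/47 (32.1% v 23.4%) | 8.7 |
| 10 : 0 | 19/55 v 9/45 (34.5% v 20.0%) | 14.5 (p = 0.11) |

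**4. Per-visit tally.** Assumptions: 30% of one arm and 10% of the other are prone to adverse events; the chance of an event per interval is h = 0.50 in prone patients and 0.05 in others; a patient stops after an event with probability s. The cumulative proportion over four intervals is 0.30(1 − 0.50⁴) + 0.70(1 − 0.95⁴) = 41% against 0.10(1 − 0.50⁴) + 0.90(1 − 0.95⁴) = 26%, a difference of 15 points whatever s is.

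Among Week 8 attendees, each type contributes (1 − hs)³·h(1 − s) to the numerator and (1 − hs)⁴ to the denominator, weighted by its share of the arm.

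| Stopping after an event | Week 8 difference, attendees | Week 8 difference, event counted where it arose |
|---|---|---|
| None | 9.0 points (18.5% v 9.5%) | 9.0 points |
| 25% in both arms | 5.7 points (12.0% v 6.3%) | 7.1 points |
| 50% v 25% | 0.3 points (6.6% v 6.3%) | 4.1 points |

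The loss due to stopping is measured from 9.0 points, not from 15: a single-interval count differs from a cumulative one even when nobody stops. These cases imply stopping for adverse events in 16% v 9% and 27% v 9%. Both exceed the plan's 10% drop-out in the first arm, so they are deliberately strong.

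**5. Exit data.** Read together, the Schedule of Events and the Safety Assessments section leave an early leaver with an examination and clinical laboratory tests at termination (routine labs include a blood count). The adverse-event inventory, the GI-event inventory (CSULGIE) and PT/PTT are not assured before six weeks.

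**The case against.** A reader might infer that the plan removes patients who stop for adverse events and discards the events of those replaced, so that harm will be understated. The documents do not say this. The contingency table is described in the singular, which fits one ever/never count. Replacement is a recruitment rule in the sample-size section. If the intent-to-treat rule covers Aim 2, it keeps anyone who leaves after the first week. Spontaneous reports are collected, visits ask about the whole interval since the last one, and there is an examination at termination, so an event between visits need not be lost. All of this stands, and it makes the understatement a risk that depends on the reading. It does not settle which reading applies: the listed weeks also parallel the visit-by-visit analysis of covariance for Aim 1.

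A second tempting step is to contrast p-values. Suppose 8 v 2 of 45 per arm stop for an adverse event and 30% of the rest report one at Week 8. The Week 8 table is 11/37 v 13/43 (p = 0.96), and stopping is 8/45 v 2/45 (uncorrected p = 0.044). The counts are assumed, Fisher's exact test gives 0.09 for the second table, and adding the stoppers to the any-event table gives 19/45 v 15/45, p = 0.38. The contrast comes mainly from changing the endpoint and does not measure the bias.

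Finally, safety is listed among the second-tier exploratory endpoints, for which the study is not powered. That limits the weight of any safety test but is no reason to leave its population undefined.

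**Conclusion.** The point holds as a gap in definition with a possible directional consequence. Aim 2's only safety and tolerability comparison lacks a population, a denominator and a cumulative rule. Under a per-visit or completer reading, unbalanced stopping for adverse events can shrink the difference between arms. Within the plan's 10% drop-out, the completers-only construction hides between 0 and 14.5 points, depending on how ten leavers split. In the stronger per-visit cases, a 9.0-point Week 8 difference falls to 5.7 or 0.3. There is no loss under a cumulative count of everyone dosed, and none in the completers-only construction when leavers split 5:5. Every one of these sizes rests on assumed event and stopping rates.

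Two parts do not rest on those assumptions: discontinuation because of an adverse event has no planned comparison by arm, and several exit assessments are not assured in patients who leave before six weeks. The exclusion of week-1 stoppers follows only if the one-week rule governs Aim 2. The definitions should be settled before unblinding, so that the choice of reading cannot depend on the data.

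**What to change.** 1. Make the main Aim 2 safety comparison any adverse event from first randomised dose to exit or Week 8. Count each patient once, among all randomised patients who took at least one dose, including those later replaced. State that the one-week minimum does not apply to it.
2. Report discontinuation because of an adverse event by arm, with the difference and its confidence interval, from the item already collected.
3. Keep the tallies at weeks 1, 2, 4 and 8 as description, with the denominator shown at each visit.
4. Request the existing adverse-event inventory, CSULGIE and CBC/PT/PTT at exit from every randomised patient who stops, whatever the week or reason. Reconcile the Schedule of Events text with the Safety Assessments section on this.
5. Reconcile the two definitions of a completer (eight weeks under Study Design, at least six under Study Procedures), since they affect who is treated as lost and replaced.

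The cost is some SAP wording, a little more analysis, and an exit request to roughly 10% of patients, some of whom will decline. No new instrument is needed.
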